5.6 Demographics and Baseline Disease Characteristics

5.6.1 Demographics

Demographic data (including age at date of informed consent, sex, race, ethnicity, height, and weight) will be summarized.

5.6.2 Medical History

5.6.2.1 General Medical History

Medical history findings will be presented in by-patient listings.

5.6.2.2 Disease Specific History

Baseline disease characteristics (such as amyloid involvement at study entry, cardiac biomarker stage at study entry, substance usage, Eastern Cooperative Oncology Group [ECOG] performance status, amyloidosis disease-related cardiac status, and amyloidosis disease-related neurologic status) will be summarized. Disease-specific history at initial diagnosis (time since initial diagnosis to first dose of MLN9708, amyloid involvement, cardiac biomarker stage, New York Heart Association classification) and the prior therapies (number of patients with prior therapy, lines of prior therapies, months from last dose of prior therapy to the first dose, best hematological response to prior therapy, and best organ response to prior therapy, type of prior therapy in the format of therapy contained, number of patients refractory to VELCADE, number of patients received VELCADE at last line of prior therapy, number of patients refractory to any line of prior therapy, number of patients refractory to last line of prior therapy) will be summarized.

All disease-specific characteristics, including agents received as prior therapy, will be presented in by-patient listings.

5.7 Treatments and Medications**5.7.1 Concomitant Medications**

Concomitant medications will be coded using the World Health Organization (WHO) Drug Dictionary. The number and percentage of patients taking concomitant medications from the first dosing date through the end of the on-study period will be tabulated by Anatomical Therapeutic Chemical (ATC) classification therapeutic subgroup and WHO drug preferred term.

Concomitant medication and procedures will be presented in by-patient listings.

5.7.2 Study Treatments**5.7.2.1 Extent of Exposure**

A patient is considered to have been treated in a cycle as long as this patient receives any amount of study drug. A treatment cycle is defined as a cycle in which the patient received any amount of study drug.

Overall treatment duration will be summarized. The extent of exposure to MLN9708 will be summarize treatment duration, the number of cycles, total amount of dose taken in mg, total number of doses taken, dose intensity, relative dose intensity. The extent of exposure to dexamethasone will summarize the number of treatment cycles. The extent of exposure will be summarized by dose level, disease groups, and for all patients. Dose intensity (mg/cycle) will be calculated on a per-cycle basis, which equals the sum of total doses (mg) received in all cycles divided by the number of treatment cycles. Relative dose intensity is defined as $100 * (\text{Total amount of dose taken} / \text{Total prescribed dose over treated cycles})$, where total prescribed dose equals [dose prescribed at enrollment * number of prescribed doses per cycle * the number of treated cycles].

5.7.2.2 Dose Modifications

The modification actions on study drug will be summarized by dose level, disease groups, and for all patients, and by cycle if there are sufficient data for analysis.

5.8 Efficacy Endpoints and Analyses

Standard response criteria will be used in this study. The efficacy parameters include hematologic response rate, organ response rate, time to hematologic response, time to organ response, duration of hematologic response, duration of organ response, time to hematologic

disease progression, time to organ disease progression, hematologic disease PFS, organ disease PFS, and 1-year overall survival (OS) rate. The response assessment criteria are defined in the study protocol appendices.

5.8.1 Efficacy Endpoints

Best overall hematologic response is defined as the best hematologic response over time. It will be calculated and summarized in 2 time frames: (1) Up to the End of Treatment (EOT) visit; and (2) Up to the initiation of alternative antineoplastic therapy or EOS.

Hematologic objective response rate (ORR) is defined as the proportion of patients who achieved a PR or better response as best overall response in the Hematological Response-Evaluable population. Additional hematologic response rates are defined in the following table in the Hematological Response-Evaluable population. All the hematologic response rates will be calculated and summarized in 2 time frames: (1) Up to the EOT visit; and (2) Up to the initiation of alternative antineoplastic therapy or EOS.

Hematologic Response Rate:	Proportion of Patients in the Hematological Response-Evaluable Population Whose Best Overall Responses Are:
CR Rate	CR
VGPR Rate	VGPR
PR Rate	PR
No Change (NC) Rate	No Change (NC)
PD Rate	PD
ORR	PR or VGPR or CR
VGPR or better	VGPR or CR

Vital organ response is defined as the best response of either heart or kidney over time. Organ-specific response is defined as the best response of each defined organ over time. Organ response rate is defined as the proportion of patients who achieved certain response (including response, no change, and PD) in the Organ Response-Evaluable population. Organ-specific response rate will be calculated in the subgroup of the Organ Response-Evaluable population with amyloid involvement of the specific organ at baseline. All the above organ response rates will be calculated and summarized in 2 time frames: (1) Up to the EOT visit; and (2) Up to the initiation of alternative antineoplastic therapy or EOS.

Time to hematologic response is defined as the time from the date of the first dose of MLN9708 to the date of first documentation of a hematologic response (PR or better). Time to vital organ response is defined as the time from the date of the first dose of MLN9708 to

MLN9708**Study C16007 Statistical Analysis Plan**

the date of first documentation of an organ response of either heart or kidney. In addition, time to best hematologic response is defined as the time from the date of the first dose of MLN9708 to the date of first documentation of the best hematologic response for each patient. The time-to-response endpoints apply only to the responders; therefore, there is no censoring. Hematologic responder is defined as a patient whose best hematologic response is PR or better. Vital organ responder is defined as a patient who demonstrates vital organ response. In addition, the responders will be determined in 2 time frames: (1) Up to the EOT visit; and (2) Up to the initiation of alternative antineoplastic therapy or EOS.

Duration of hematologic response is defined as the time from the date of first documentation of a hematologic response (PR or better) to the date of hematologic PD. Duration of vital organ response is defined as the time from the date of first documentation of an organ response of either heart or kidney to the date of organ PD. The duration-of-response endpoints apply only to the responders. However, the responders will be determined in two time frames: (1) Up to the EOT visit; and (2) Up to the initiation of alternative antineoplastic therapy or EOS. Patients will be censored in any of the following scenarios:

- If the patient starts an alternative antineoplastic therapy before the documentation of PD, then he or she will be censored at the date of the last available response assessment before the alternative antineoplastic therapy.
- If the patient has no documented PD and has not started alternative antineoplastic therapy and is still alive at the time of analysis, he or she will be censored at the date of the last available response assessment.
- If the patient died before the documentation of PD and had not started any alternative antineoplastic therapy, he or she will be censored at the date of the last available response assessment.

Time to hematologic disease progression is defined as the time from the date of the first dose of MLN9708 to the date of first documented hematologic PD. Time to organ disease progression is defined as the time from the date of the first dose of MLN9708 to the date of first documented organ PD. Patients will be censored in any of the following scenarios:

- If the patient starts an alternative antineoplastic therapy before the documentation of PD, then he or she will be censored at the date of the last available response assessment before the alternative antineoplastic therapy.

MLN9708**Study C16007 Statistical Analysis Plan**

- If the patient has no documented PD and has not started alternative antineoplastic therapy and is still alive at the time of analysis, he or she will be censored at the date of the last available response assessment.
- If the patient died before the documentation of PD and had not started any alternative antineoplastic therapy, he or she will be censored at the date of the last available response assessment.

Hematologic disease PFS is defined as the time from the date of the first dose of MLN9708 to the date of documented hematologic PD or any death. Organ disease PFS is defined as the time from the date of the first dose of MLN9708 to the date of documented organ PD or any death. Patients will be censored in any of the following scenarios:

- If the patient starts an alternative antineoplastic therapy before the documentation of PD, then he or she will be censored at the date of the last available response assessment prior to the alternative antineoplastic therapy.
- If the patient has no documented PD and has not started alternative antineoplastic therapy and is still alive at the time of analysis, he or she will be censored at the date of the last available response assessment.

OS is defined as the time from the date of the first dose of MLN9708 to the date of death. Patients without documentation of death at the time of analysis will be censored at the date last known to be alive. One-year OS rate is defined as the patient survival rate at 1 year after the date of the first dose of MLN9708.

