8.1.6 Efficacy Analysis

Standard response criteria will be used in this study.^(53, 54) The patients treated at doses other than the dose in the expansion cohorts may be combined together for analysis and for presentation in the tables and figures.

The efficacy parameters include the organ response rate and organ improvement rate, overall hematologic response rate, time to hematologic and organ response, duration of hematologic and organ response, time to hematologic and organ response, hematologic and organ disease free progression, and 1-year survival rate.

The organ response and improvement rate will be analyzed based on the organ response-evaluable population. Estimates of the organ response rate will be presented with 2-sided 95% exact binomial confidence intervals.

The hematologic response rate will be analyzed based on the hematologic response-evaluable population and presented with 2-sided 95% exact binomial confidence interval.

Time to organ or hematologic response is defined as the time from the date of the first dose of MLN9708 to the date of first documentation of a confirmed organ or hematologic response, respectively.

Duration of organ or hematologic response is defined as the time from the date of first documentation of a confirmed organ or hematologic response to the date of confirmed organ or hematologic disease progression, respectively.

Time to organ or hematologic disease progression is defined as the time from the date of the first dose of MLN9708 to the date of first documented organ or hematologic disease progression.

[figure not shown]
Organ or hematologic disease progression free survival is defined as the time from the date of the first dose of MLN9708 to the date of confirmed organ or hematologic disease progression or death, respectively.

One-year survival is defined as the patient survival probability at 1 year after the date of first dose of MLN9708.

Time to response, duration of response, time to progression, PFS, and survival may be analyzed using standard survival analysis techniques based on Kaplan-Meier estimates if appropriate.

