5. STATISTICAL METHODOLOGY

Analyses will be primarily descriptive in nature. No formal statistical tests will be performed. Summary tabulations will be presented that display the number of observations, mean, standard deviation, median, minimum, and maximum for continuous variables, and the number and percentage (calculated using nonmissing values) per category for categorical data, unless specified otherwise.

Patients will be analyzed at the dose level to which they were originally assigned, including those who receive subsequent treatment at a lower dose level.

The analyses for the clinical study report (CSR) will be conducted after 75% of patients have PD or 12 months after last patient is enrolled, whichever occurs first in the study. At that time, all relevant data will be queried and cleaned; a database snapshot will be taken and used for the CSR. Additional follow-up treatment data will be entered into the database through study termination. Analyses may be updated based on additional information. An addendum to the CSR may be written if warranted based on these analyses. If deemed appropriate, however, the sponsor may decide to perform the analyses for CSR at the end of the study (EOS), which is approximately 2 years after the last patient is enrolled.

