5.8.2 Efficacy Analyses

The hematologic response (CR, VGPR, PR, no change [NC], PD) rate will be tabulated and analyzed based on the Hematologic Response-Evaluable population and presented with a 2-sided 95% exact binomial confidence interval. In addition, the overall hematologic response rates up to the end of Cycle 3 and up to the end of Cycle 6 will also be tabulated and analyzed in a similar way.

Vital organ response rate will be tabulated and analyzed based on the Organ Response-Evaluable population. Organ-specific response rate will be tabulated and analyzed based on in the subgroup of the Organ Response-Evaluable population with amyloid involvement of the specific organ at baseline. Estimates of the organ response rate will be presented with 2-sided 95% exact binomial confidence intervals.

MLN9708**Study C16007 Statistical Analysis Plan**

Best hematologic response, time to hematologic response, time to best hematologic response, duration of hematologic response, time to hematologic PD, hematologic PFS, and OS will be presented in a by-patient listing. Vital organ response, organ-specific response, time to vital organ response, duration of vital organ response, time to organ PD, organ PFS, and OS will be presented in a by-patient listing.

Time to hematologic response, time to best hematologic response, duration of hematologic response, time to hematologic PD, hematologic PFS, and OS (1-year OS rate) will be analyzed using standard survival analysis techniques based on Kaplan-Meier estimates, if appropriate.

Raw values of serum M-protein, urine M-protein, serum free light chain (FLC), and the difference between amyloid-forming and nonamyloid-forming free light chain (dFLC), as well as the change from baseline, will be presented in by-patient listings. A waterfall plot will be generated to display the maximum change from baseline in dFLC.

QOL will be assessed for patients in the expansion cohorts only using the European Organisation for Research and Treatment of Cancer Quality of Life Questionnaire-Core 30 (EORTC-QLQ-C30, multiple myeloma module). Descriptive statistics will be presented for both the actual values and the changes from baseline in EORTC-QLQ-C30 assessment over time. EORTC-QLQ-C30 assessments will be analyzed to determine if hematologic response to therapy is accompanied by measurable improvement in QOL.

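### Kaplan-Meier on responders only makes the time-to-hematologic-response curve end at 100% whatever the response rate, and an early data cut can shorten its median

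*SAP*

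**What the plan says.** SAP 5.8.1 defines time to hematologic response, time to best hematologic response and time to vital organ response, each from the first dose. It then states: "The time-to-response endpoints apply only to the responders; therefore, there is no censoring". Membership of that set depends on the outcome: "Hematologic responder is defined as a patient whose best hematologic response is PR or better". It is determined over two time frames, one ending at the EOT visit and the other at alternative antineoplastic therapy or end of study.

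SAP 5.8.2 names the endpoints for survival methods: "Time to hematologic response, time to best hematologic response, duration of hematologic response, time to hematologic PD, hematologic PFS, and OS (1-year OS rate". They are to be analysed "using standard survival analysis techniques based on Kaplan-Meier estimates, if appropriate". The organ endpoints are not in that list. For them the same section plans a by-patient listing: "time to vital organ response, duration of vital organ response, time to organ PD, organ PFS, and OS will be presented".

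Protocol 8.1.6 is more general: "Time to response, duration of response, time to progression, PFS, and survival may be analyzed using standard survival analysis techniques". It gives neither an analysis set nor a censoring rule for time to response.

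SAP section 5 places the CSR analyses "after 75% of patients have PD or 12 months after last patient is enrolled, whichever occurs first in the study". It also allows later updates, a CSR addendum, or running the CSR analyses at end of study instead.

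**The concern.** Kaplan-Meier earns its place by using patients whose event has not yet been seen. Here every such patient is removed before the estimator is applied. Two things follow.

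First, the curve carries no information about how many patients respond. SAP 5.4.4 plans summaries by dose level, by expansion cohort, at the MTD and overall. On this endpoint, a cohort in which few respond and one in which most respond both rise to 100%. A reader who takes the curve for the probability of response by a given time will be misled.

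Second, a patient still at risk at the cut who would respond later is deleted, and late responders are the ones most likely to be deleted. The observed distribution is right-truncated, so its median can fall but cannot rise. Protocol 1.1.1 stresses that speed of response matters in this disease, so a median that looks too fast is not harmless.

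**Working it through.** The documents give no expected time to response and no hematologic response rate, so there is no stated figure to reproduce. The response times and counts below are assumptions.

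**1. The endpoint at 100%.** With n responders and no censoring, the Kaplan-Meier product telescopes. After the k-th response, S = (n − k)/n, so 1 − S = k/n, and 1 − S = 1 at the last responder. This is an identity.

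Assumed example: 13 responders, with first responses at Cycles 1 to 6 numbering 4, 3, 2, 2, 1, 1, and non-responders followed through Cycle 6.

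| Cycle | Responders only (n = 13) | All patients (13 of 26) | All patients (13 of 29) |
|---|---|---|---|
| 1 | 31% | 15% | 14% |
| 2 | 54% | 27% | 24% |
| 3 | 69% | 35% | 31% |
| 4 | 85% | 42% | 38% |
| 5 | 92% | 46% | 41% |
| 6 | 100% | 50% | 45% |
| Median | 2 cycles | 6 cycles | not reached |

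The responders-only column is the same whether the denominator is 26 or 29. The all-patient curve levels off at the response rate.

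**2. Effect of the data cut.** Inputs from the documents:

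- Enrolment of about 24 months (Protocol 4.3).
- Hematologic assessment after every 28-day cycle (Protocol Summary).
- Patients without hematologic response after 3 + 3 cycles leave treatment (Protocol 4.1). Without delays this is 6 × 28 = 168 days, or 5.5 months.
- A maximum of 12 cycles in general, 336 days or 11.0 months (Protocol 4.3).
- A cut at the earlier of 75% PD and 12 months after last enrolment, which is month 36 from first enrolment.

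Assume uniform entry over 24 months. For a cut at month C (24 or later), a response at time t is seen with probability min(24, C − t)/24. The density of observed times is then proportional to f(t) × min(24, C − t)/24, and the observed median is the midpoint of that distribution.

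*Exponential times, f(t) = λe^(−λt), λ = ln 2 / true median:*

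| True median | Cut at month 24 | Month 30 | Month 36 |
|---|---|---|---|
| 6 months | 3.8 (−36%) | 4.7 (−22%) | 5.3 (−12%) |
| 9 months | 4.6 (−49%) | 5.7 (−36%) | 6.8 (−24%) |

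At month 36, about 92% and 82% of eventual responses have been seen. At month 24 the shares are about 66% and 54%.

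*First response confined to Cycles 1 to 6* (assumed shares 30%, 15%, 10%, 20%, 15%, 10%; true median 3 cycles = 2.8 months): observed median 1.8 months at a month-12 cut and 2.8 from month 18 on. From month 30 no responder is missed, because the last patient has then been followed for 6 months, longer than 5.5.

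*Best response spread evenly over Cycles 1 to 12* (true median 5.5 to 6.4 months): observed 3.7 at month 12 and 4.6 at month 18, with no clear shift from month 24.

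Cuts at months 12 and 18 would require the PD trigger to fire during enrolment, so they are extreme cases.

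**The case against.** The case for leaving the plan alone has several parts.

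- **Non-responders are not lost.** Evaluable non-responders stay in the denominator of the response rate, which has an exact 95% interval. SAP 5.8.2 also tabulates overall hematologic response rates to the end of Cycle 3 and of Cycle 6. This stands in part: those rates supply two points of the all-patient curve. They do not change what the Kaplan-Meier figure shows.
- **The stopping rule bounds first hematologic response.** This stands. It is why the shift can be nil at the later cut, and why exponential times with medians of 6 or 9 months are a poor model for first response before EOT. They would place 53% and 65% of responses after 5.5 months.
- **The analysis can be updated.** SAP section 5 allows this. It reduces the truncation but not the 100% endpoint.
- **The study is phase 1, the endpoint secondary and descriptive, and Kaplan-Meier is conditional on being appropriate.** True, and this limits the severity. But no criterion for appropriateness is given, so the qualifier does not settle the matter.

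A reader might infer that the SAP contradicts the protocol. The documents do not support that. Protocol 3.2 and 8.1.6 define the interval without naming an analysis set, so the SAP fills a silence, although SAP section 6 does not mention the restriction.

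A reader might also infer that slow organ responses are being cut from a curve. No organ curve is planned. The protocol remark in 1.1.1 about delayed organ improvement goes on to present hematologic response as the short-term marker.

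**Conclusion.** The point holds for time to hematologic response and time to best hematologic response. As planned, the Kaplan-Meier curve is the empirical distribution among patients selected on the outcome. It reaches 100% by construction and cannot be used to compare groups with different response rates. This part needs no assumption.

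The effect of the cut is conditional. It is nil at 12 months after last enrolment if first responses fall within six cycles. It matters if the 75%-PD trigger fires early, for time to best response under an early cut, or for late responses counted in the second time frame. Under exponential times and uniform 24-month accrual, true medians of 6 and 9 months read about 5.3 and 6.8 at that cut, and 3.8 and 4.6 at month 24 from first enrolment.

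Two stronger readings fail. An early cut does not always shorten the median. And biases of about −32% and −48% for those medians require every patient to have exactly 12 months of follow-up; with 24 months of accrual, follow-up since first dose at that cut ranges from 12 to 36 months.

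**What to change.** In SAP 5.8.1 and 5.8.2:

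- Estimate time to hematologic response by cumulative incidence in the Hematologic Response-Evaluable population. Treat death, PD and alternative antineoplastic therapy as competing events, and censor patients still at risk at their last assessment.
- Report responders-only time to response and time to best response as median and range, labelled as among responders, without a Kaplan-Meier curve.
- Leave the by-patient listing of time to vital organ response as it is; this point does not call for a change there.

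The cost is SAP wording and one extra figure from data already collected. The drawback is that the curve levels off at the response rate, so a median may not be reached.

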1. BACKGROUND AND STUDY RATIONALE

1.1 Scientific Background

1.1.1 Disease Under Treatment

Primary systemic light chain (AL) amyloidosis is a progressive disorder caused by proteotoxic light chain proteins produced by a clonal plasma cell dyscrasia.^(1, 2, 3) The plasma cell dyscrasia is characterized by monoclonal plasma cells in the bone marrow and the production of excess monoclonal immunoglobulin light-chains that tend to misfold, form aggregates, and deposit as unique amyloid fibrils in visceral organs. Tissue damage is caused when these light chain aggregates interact with cells and when they form large amounts of amyloid fibrils, insoluble pleated β sheet filaments in fibrils that cause end-organ dysfunction.⁽⁴⁾ While the disease is a clonal plasma cell disease like multiple myeloma, the M-protein is often not an intact immunoglobulin and the clonal plasma cells are present at a low percentage in the bone marrow and are predominantly λ rather than κ restricted (κ -to- λ ratio is 1:4).^(1, 5, 6)

Amyloidosis is a rare disease where early diagnosis and treatment are key to patient outcomes. Unfortunately, late diagnosis is still a major problem. Extracellular deposition of the fibrils ultimately results in an accumulation that disrupts normal tissue structure and function notably in the heart, kidneys, peripheral nervous system, and gastrointestinal tract with liver and soft tissues.⁽¹⁾ This progressive accumulation ultimately leads to organ dysfunction, organ failure, and finally death, often due to cardiac causes. The disease carries a poor prognosis which is predominantly influenced by the patient's performance status and extent of organ involvement, particularly cardiac involvement, at diagnosis. One-fourth of patients present with clinical involvement of 1 organ; however, the majority present with clinical involvement of more than one.^(1, 7) Renal dysfunction is the most common clinical manifestation while liver involvement is reported but not very common. The severity of the cardiac involvement ultimately dictates the prognosis. Notably the majority of patients with AL amyloidosis die from a cardiac death, which is often sudden.⁽⁸⁾

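### Duration of hematologic response censors deaths without documented PD, so the planned Kaplan-Meier estimate can overstate time alive in response, by an amount the documents do not determine

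*SAP*

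**What the plan says.** SAP 5.8.1 measures duration of hematologic response from the first documented PR or better to hematologic PD, in responders only. Three situations lead to censoring. The third is death: "If the patient died before the documentation of PD and had not started any alternative antineoplastic therapy", then "he or she will be censored at the date of the last available response assessment". The same rule covers duration of vital organ response and both time-to-progression endpoints.

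PFS is handled differently. In the same section, hematologic PFS ends at "the date of documented hematologic PD or any death" and organ PFS at "the date of documented organ PD or any death".

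SAP 5.8.2 states that duration of hematologic response, time to hematologic PD, hematologic PFS and OS "will be analyzed using standard survival analysis techniques based on Kaplan-Meier estimates", if appropriate. Duration of vital organ response and time to organ PD are named there only for a by-patient listing.

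The protocol (3.2 and 8.1.6) also ends duration of response at "confirmed organ or hematologic disease progression, respectively", with no mention of death. The SAP therefore implements the protocol's definition.

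**The concern.** Kaplan-Meier treats a censored patient as someone who would have gone on to the event at the same rate as those still followed. A responder who has died cannot progress, so the resulting curve describes durability as if death did not occur.

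Two features of this trial make such deaths plausible. Hematologic PD (Protocol 15.8) rests on M-protein, free light chains and immunofixation. It has no clinical or organ component, so a cardiac death with controlled light chains can never become a hematologic PD event. And Protocol 1.1.1 says that "the majority of patients with AL amyloidosis die from a cardiac death", often suddenly. In the planned curve such a patient looks the same as one who is alive and still responding.

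PFS does not fill the gap. It runs from first dose and is not confined to responders, so it does not show how long a response lasts once achieved. What is at stake is the durability figure for a secondary endpoint, which readers may well take as time spent alive and in response.

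**Working it through.** **The plan's own figures.** The documents give no expected duration of response, no expected time to progression and no rate of death without PD. The only design figures are the two organ-response probabilities in SAP 5.1, and they reproduce:

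- 1 - 0.65^8 - 8 × 0.35 × 0.65^7 = 0.831 (stated 83%)
- 1 - 0.80^14 - 14 × 0.20 × 0.80^13 = 0.802 (stated 80%)

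They do not bear on this point.

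**Size as a function of the death share.** Assume constant, independent hazards after response: h_P for PD and h_D for death without PD.

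- Share of first events that are deaths: q = h_D/(h_P + h_D)
- Median with deaths censored: ln 2/h_P
- Median with death as an event: ln 2/(h_P + h_D)
- Ratio of the two: (h_P + h_D)/h_P = 1/(1-q)

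| q | Inflation of the median |
|---|---|
| 5% | 1.05 |
| 10% | 1.11 |
| 25% | 1.33 |
| 50% | 2.00 |

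**Check by simulation.** Assumptions: 20 responders, assessments every 6 weeks (the follow-up interval in the Schedule of Events), follow-up uniform over 12 to 36 months, PD-only median 18 months, censoring at the last assessment, 1,500 simulated trials per row. With deaths censored, the typical median was 17.9 months and the mean 12-month estimate 65% in every row.

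| Assumed median time to death without PD | q | Median, death as event | 12-month estimate, death as event |
|---|---|---|---|
| 96 months | 16% | 15.2 months | 60% |
| 48 months | 27% | 12.4 months | 55% |
| 24 months | 43% | 9.7 months | 46% |

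**Illustration using figures in the protocol.** Protocol 1.1.1 cites a bortezomib study in which 78% of responders had a response longer than one year. Assume this can be read as a PD-only rate; how that study handled deaths is not stated. Then h_P = -ln(0.78)/12 = 0.0207 per month, and the median is 33.5 months. The same section gives a median survival of 13.2 months from diagnosis, a hazard of ln 2/13.2 = 0.0525 per month. Suppose responders die without PD at a fraction of that hazard:

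| Fraction of 0.0525 | q | Median, death as event | 12-month duration (78% with deaths censored) |
|---|---|---|---|
| 10% | 20% | 26.7 months | 73% |
| 25% | 39% | 20.5 months | 67% |
| 50% | 56% | 14.8 months | 57% |
| 100% | 72% | 9.5 months | 42% |

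The last row is a ceiling, since that hazard comes from all patients at diagnosis and not from responders. None of these rows is a prediction.

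**The case against.** The strongest defence concerns what the endpoint is meant to measure. Time to hematologic PD among responders describes control of the clone. A death from existing cardiac damage is not a hematologic relapse, and the protocol chose this definition in advance. That stands: the rule is a legitimate choice and not an error. But it answers only one of the two questions that a reader will have about durability.

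The second argument is that q may be small. The trial excludes risk Stage III and NYHA class III or IV, and requires ECOG 0 to 2 and an ejection fraction of at least 40% (Protocol 5.1 and 5.2). Protocol 1.1.1 says that hematologic and organ responses predict survival. This also stands, and it is why mortality from diagnosis cannot be carried over to responders. It lowers q without making it zero, because Stage II patients and patients with heart involvement are eligible.

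Third, the deaths are not hidden. Duration, PFS and OS all appear in by-patient listings (SAP 5.8.2), so a reader could find responders who died without PD. A listing is still not a summary, and neither a count nor a death-inclusive estimate is planned.

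Fourth, precision is low. With 20 responders, one standard error of a 65% estimate is about sqrt(0.65 × 0.35/20) = 0.107. A gap of 5 points lies well inside that. The shift is nonetheless systematic and upward, and is not removed by wider intervals.

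A reader might also infer that time to progression needs the same change. The documents do not support that. Excluding death is part of that endpoint's definition, and the SAP pairs it with PFS from the same origin counting any death. The numerical effect is also modest: with assumed hazards of 0.03 per month for PD and 0.015 to 0.03 for death, the 12-month figure is 30% by 1 minus Kaplan-Meier against a cumulative incidence of 28% to 26%.

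**Conclusion.** The point holds for duration of hematologic response. The censoring rule, combined with Kaplan-Meier and no death-inclusive version, can overstate how long responders remain alive in response. Under constant independent hazards the median is inflated by 1/(1-q), from about 5% at q = 5% to a doubling at q = 50%. The documents do not give q.

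A reader might infer that responses will look much longer than patients experience. For example, the hazards of 0.03 for PD and 0.015 to 0.03 for death give a median of 23 months against 15 to 12, and a 12-month duration of 70% against 58% to 49%. Those hazards assume that 33% to 50% of first events are deaths, and nothing in the documents supports that share among selected responders.

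Nor does the Kaplan-Meier argument extend firmly to organ duration, which SAP 5.8.2 names for listing only. There is no conflict between SAP and protocol. The endpoint is secondary and descriptive in a single-arm phase 1 study without formal tests, so no sample size or decision rule changes. This is a worthwhile, inexpensive improvement.

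**What to change.** Keep the planned analysis. In SAP 5.8.1 and 5.8.2, add:

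- Duration of hematologic response with hematologic PD or death from any cause as the event, shown beside the planned estimate. Leave censoring at alternative antineoplastic therapy unchanged, so that the two versions differ only in how death is handled. Cumulative incidence of PD with death as a competing event is an acceptable alternative.
- The number of responders censored because they died without documented PD.
- The same two items for duration of vital organ response, if it is summarised beyond the listing.

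Time to progression needs no change. Death dates are already required for PFS and OS, so no new data are collected. The cost is one extra analysis, and the quoted duration will be less favourable if any responder dies without PD.
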